7.2. Study Endpoints

7.2.1. Co-Primary Endpoints

- Correlation of % change in spleen volume at Week 24 compared to baseline versus final titrated dose.
- Correlation of % change in Total Symptom Score as measured by the modified MFSAF v2.0 diary at Week 24 compared to baseline versus final titrated dose.

[figure not shown]
7.2.2. Safety Endpoints:

- Safety and tolerability will be assessed by monitoring the frequency, duration and severity of adverse events, performing physical examinations, collecting vital signs, collecting laboratory data for hematology, serum chemistry, and coagulation parameters through Week 156. In addition, analyses will include:
 - Proportion of subjects with new onset Grade 4 thrombocytopenia events as assessed by CTCAE v4.03.
 - Proportion of subjects with new onset Grade 2 or higher hemorrhage as assessed by CTCAE v4.03.

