5. STUDY OBJECTIVES AND PURPOSE

5.1. Primary Objective

- To determine the effects of ruxolitinib on spleen volume and symptom burden in patients with primary myelofibrosis (PMF), post polycythemia vera-myelofibrosis (PPV-MF) and post essential thrombocythemia-myelofibrosis (PET-MF) who have Baseline platelet count of $50 \times 10^9/L$ to $100 \times 10^9/L$.
- To determine the safety and tolerability of ruxolitinib in patients with PMF, PPV-MF and PET-MF who have Baseline platelet count of $50 \times 10^9/L$ to $100 \times 10^9/L$.

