5.2. Secondary Objectives

- To determine an appropriate dosing strategy for patients with low platelets.
- To determine the long-term safety and efficacy effects of ruxolitinib in patients with PMF, PPV-MF, and PET MF who have a baseline platelet count of $50 \times 10^9/L$ to $100 \times 10^9/L$.

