8. TREATMENT OF SUBJECTS

8.1. Treatment Arms and Study Drug Administration

All subjects will begin dosing at 5 mg bid ruxolitinib. Doses should be taken morning and evening, approximately 12 hours apart, and without regards to food.

Dose increases will be allowed for subjects with adequate platelet counts, and mandatory dose reductions and interruptions will be required for declining platelet counts, declining ANC levels or Grade 2 and higher hemorrhage events. See [Section 8.6](#), Dose Adjustments.

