8.3. Randomization and Blinding

Not applicable, study is open label and single arm.

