8.6.1. Dose Increases

Dose increases are optional.

During the core treatment phase, doses of ruxolitinib may be increased in 5 mg qd increments up to a dose of 10 mg bid starting at the Week 4 visit and at subsequent study visits. Dose increases can occur no more frequently than every 4 weeks, and only if:

- Platelet count was always $\geq 40 \times 10^9/L$ since the last scheduled study visit
- Platelet count, if decreased since the last scheduled study visit, is decreased by no more than 20% of the platelet count at the last scheduled visit
- No dose decreases or holds for safety have occurred during the preceding 4-week interval
- $ANC > 1.0 \times 10^9/L$ since the last scheduled study visit.
- For subjects with prior \geq Grade 2 hemorrhage events, please see below under [Section 8.6.3.4](#), Restarting with Resolution of Hemorrhage Events

Doses may not exceed 10 mg bid except in subjects who continue to meet the above dose escalation criteria, and who have, in addition, a PGIC score of 3 (minimally improved) to 7 (very much worse) while receiving 10 mg bid. Such subjects may continue dose escalation to a maximum dose of 15 mg bid. Note that when a 5 mg qd increment is added, creating a regimen such as 5 mg/10 mg, the higher dose should be taken in the evening and the lower dose in the morning.

During the extended treatment phase, doses of ruxolitinib may be increased in 5 mg qd increments up to a dose of 25 mg bid if the subject meets the above dose escalation criteria, or per the investigator's discretion.

Doses may never exceed 25 mg bid.

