8.6.2. Mandatory Dose Interruptions, Dose Discontinuations and Dose Reductions

Dosing must be held if any of the following occur:

- Platelet counts decline below $25 \times 10^9/L$ (dosing must be interrupted immediately. A repeat assessment should be performed as soon as feasible, but follow-up platelet values to trigger the restart guidelines from [Section 8.6.3](#) may only follow beginning at least 3 days later).
- ANC declines to $< 0.5 \times 10^9/L$.
- Ongoing Grade 2 or higher hemorrhage event, regardless of causality.

The dose must be reduced for a confirmed platelet count $< 35 \times 10^9/L$ as follows:

- An observation of platelets between $25 \times 10^9/L$ and $35 \times 10^9/L$ should trigger a repeat laboratory measurement of platelet counts. Dosing need not be adjusted until the results of the confirmatory test are known.
- The reduction will be based on the current dose, and on the rapidity with which counts declined to the $< 35 \times 10^9/L$ level and are $\geq 25 \times 10^9/L$ (see [Table 2](#)).
- Subjects who have implemented a dose reduction because of platelets falling below $35 \times 10^9/L$ DO NOT need to further decrease their dose provided the platelet count remains $\geq 25 \times 10^9/L$ even if they remain below $35 \times 10^9/L$.
- Mandatory dose reductions are summarized in [Table 2](#).

Table 2: Mandatory Dose Reductions and Dose Holds for Safety

| Thrombocytopenia | |
|--|---|
| Platelet Count at Time of Decline | Action with Respect to Dose |
| $\geq 35 \times 10^9/L$ throughout study | Continue on dose established according to Section 8.6.1 |
| $< 35 \times 10^9/L$ and $\geq 25 \times 10^9/L$ (confirmed by repeat lab), and platelet count decline is $>20\%$ from prior visit | Decrease current dose level by 5 mg bid or to a dose of 5 mg qd if currently receiving 5 mg bid. If current dose is 5 mg qd, can continue at that dose. |
| $< 35 \times 10^9/L$ and $\geq 25 \times 10^9/L$ (confirmed by repeat lab), and platelet count decline is $\leq 20\%$ from prior visit | Decrease current dose level by 5 mg qd or to a dose of 5 mg qd if currently receiving 5 mg bid. If current dose is 5 mg qd, can continue at that dose. |
| $< 25 \times 10^9/L$ | Must hold dosing |
| Active Hemorrhage | |
| Worst CTCAE Grade | Action with Respect to Dose |
| Grade 1 | May continue dosing (frequent platelet counts recommended) |
| Grade ≥ 2 | Must hold dosing |
| Neutropenia | |
| ANC at Time of Decline | Action with Respect to Dose |

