| $< 0.5 \times 10^9/L$ | Must hold dosing |

NOTE: Investigators may also decrease the dose for any reason based on their clinical judgment, including taking a more conservative approach to hematological abnormalities or because of nonhematologic safety findings. Dose re-escalation will follow the guidelines provided in [Section 8.6.1](#) (Dose Increases).

8.6.3. Restarting or Increasing Ruxolitinib after Recovery of Platelet or ANC Levels or Resolution of Hemorrhage

Note that the restarting and re-escalation doses in this section are the maximum allowed under this protocol. Individual investigators may elect to adopt a more cautious approach to restarting or escalating doses at their discretion, but they may not restart sooner or re-escalate more rapidly than outlined in this section.

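### The co-primary correlation relates Week 24 change to a dose reached by titration: it is an association, not a dose effect, and alone it cannot answer the primary objective

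*Protocol*

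**What the plan says.** Protocol 5.1 gives the first primary objective as "To determine the effects of ruxolitinib on spleen volume and symptom burden in patients with primary myelofibrosis" and related diseases. The co-primary endpoint in Protocol 7.2.1 is "Correlation of % change in spleen volume at Week 24 compared to baseline versus final titrated dose", with a parallel correlation for TSS.

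Protocol 12.2.1 tests each Pearson r two-sided at 5% and rejects on its absolute value (0.16 at n = 150). TSS is tested only if spleen volume rejects. SAP 7.1 uses the same unadjusted r. Its sensitivity analyses are a per-protocol repeat and a possible multiple imputation. Protocol 12.4 and SAP 4.3, including the Figure 1 title, call r a dose-effect correlation.

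On how dose arises:
- Protocol 8.1: "All subjects will begin dosing at 5 mg bid ruxolitinib". Protocol 8.3, on randomization: "Not applicable, study is open label and single arm".
- Protocol 8.6.1: "Dose increases are optional", subject to platelet, ANC and hemorrhage conditions. Going above 10 mg bid in the core phase also needs a qualifying PGIC score.
- Protocol 8.6.2: "The dose must be reduced for a confirmed platelet count" below 35 × 10⁹/L. Dosing is held for lower platelets, low ANC or Grade 2 or higher bleeding. The note to Table 2 adds: "Investigators may also decrease the dose for any reason based on their clinical judgment".
- SAP 5.9.3.1: final titrated dose is the average daily dose over Days 141 to 168, excluding interruptions, or over the last 28 days of dosing data for early discontinuers.

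The overall mean percent change is to be estimated with a 95% CI (Protocol Synopsis and 12.4; SAP 4.3). As an endpoint, percent change is secondary (Protocol 7.2.3) and summarised descriptively (SAP 7.2).

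**The concern.** Final dose here behaves partly as an outcome. A patient with more marrow reserve can climb; one whose platelets fall must come down; one who feels little better at 10 mg bid may be allowed higher. Each of these may also bear on spleen and symptom change. An unadjusted r mixes any effect of dose with the reasons patients reached it, and neither sensitivity analysis addresses how dose was set.

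Two misreadings are at stake. A significant r could be reported as evidence that more drug produces more response. And because r takes no account of the average change, a null r could be read as no effect, or a significant r as efficacy, when the primary objective asks about change in these patients overall. A positive r (higher dose, less improvement) would also reject the null and allow the TSS test to proceed.

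**Working it through.** **1. The plan's own figures.** Inputs: n = 150 and two-sided 5% (Protocol 12.2.1, 12.4).

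Critical |r| = t/√(n − 2 + t²), with t = 1.976 on 148 df: 1.976/√(148 + 3.905) = 0.160. Stated: 0.16.

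Power = Φ{[atanh(ρ) + ρ/(2(n − 1)) − atanh(0.1603)]·√(n − 3)}; the opposite tail is negligible.

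| True ρ | Computed | Stated |
|---|---|---|
| 0.30 | 96.4% | 96% |
| 0.25 | 87.4% | 87% |
| 0.20 | 69.3% | 69% |

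CI half-width for mean spleen change: 1.96 × 19/√150 = 3.04 points. Stated: about 3%. The arithmetic is sound.

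**2. What varies dose.** Starting dose is constant and nothing is randomised, so the spread in the Day 141–168 average is entirely post-baseline. The written drivers are platelets, ANC, hemorrhage, optional increases, discretionary decreases and PGIC. PGIC (Appendix 5) asks about change in myelofibrosis symptoms, close to the second co-primary. The Week 24 TSS window (SAP Table 4) also starts at Day 141, so it overlaps the dose window.

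**3. What that can do to r.** With standardised variables, let a common cause U have coefficient a on dose and b on percent change, and let dose have coefficient c on percent change. Then r = c + ab. The documents give none of these values, so the following are assumptions:
- No dose effect (c = 0) and b = −a: a = 0.2, 0.3, 0.4, 0.5 gives r = −0.04, −0.09, −0.16, −0.25. An association is created and reaches the critical value at a = 0.4.
- A real coefficient c = −0.30 and b = a (poorer responders escalated): a = 0.2, 0.3, 0.4, 0.5 gives r = −0.26, −0.21, −0.14, −0.05. The association is hidden. At a = 0.6, r = −0.30 + 0.36 = +0.06 and the sign reverses.

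These show possibility, not likelihood.

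**4. Whether r addresses the primary objective.** Adding a constant to every patient's percent change leaves r unchanged, so a benefit equal at all doses gives a true r of zero. Simulation with 20,000 trials, n = 150, SD 19% and an assumed spread of doses unrelated to response:

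| Assumed mean change | Correlation test rejects | One-sample test of mean rejects |
|---|---|---|
| −5% | 5% | 89% |
| −10% | 5% | 100% |
| −20% | 5% | 100% |

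**The case against.** Several parts of the defence stand.

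- **The powered quantity.** A reader might infer that the sample size was computed for something other than what is tested. It was not: SAP 4.3 defines its dose-effect correlation as percent change against final titrated dose, and the figures reproduce.
- **The plan as a whole.** A reader might infer that the trial cannot address its primary objective. That goes too far. The Synopsis attaches the overall drug effect to the estimate across all patients, with a CI. The Table 14.2.2.1 shell carries p-values for overall Week 24 change in spleen volume, and Table 14.2.3.1 follows it for TSS. Nor does any text equate rejection with benefit; SAP 3.2 says only that the correlation is not zero.
- **Other causal wording.** Protocol 4.1.5 links the observed effect to titration, and SAP 5.9.3.4 speaks of dose-response analyses. Neither interprets r: the first compares a TSS time course with another study, the second is a rule on which dosing data to use.
- **Response feedback is narrow.** PGIC applies only above 10 mg bid in the core phase. Below that the written criteria are hematologic and safety-based; response-driven choice is an inference from optional increases and the Protocol 8.6 aim of maximum benefit.
- **Incomplete text.** Part of SAP 5.4.1 is redacted, and Protocol 12.2.3 is listed in the contents but not in the supplied text. SAP 9.5 plans PK-PD work on efficacy. Statements of absence cover visible text only, though the SAP table list shows just the two sensitivity analyses.

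The study is also Phase 2 and described as exploratory, which limits the severity. None of this makes achieved dose an assigned dose, or says which analysis carries the efficacy conclusion.

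**Conclusion.** The concern holds as a fault of label and interpretation. The powered r is a valid descriptive association between Week 24 change and achieved dose. It is not a causal dose effect, its rejection in either direction does not show benefit, and alone it cannot answer the primary objective. This follows from the dosing rules and needs no numerical assumption. The coefficients in the illustration are assumed; the size and net direction of any bias cannot be derived from the documents, and a reader should not infer that r is biased one particular way.

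The better-matched quantity is already planned: mean percent change, with a half-width of about 3 points for spleen volume at n = 150 and SD 19%. It is placed as secondary or descriptive, and no visible text rests the conclusion on it. The correlation keeps a proper role under the secondary objective: "To determine an appropriate dosing strategy for patients with low platelets".

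**What to change.** 1. In Protocol 12.4 and SAP 4.3, including the Figure 1 title, replace *dose-effect correlation* with *association with achieved (titrated) dose*. In Protocol 12.2.1 and SAP 7.1, state that r is not interpreted as a causal dose effect and that a positive r (higher dose, less improvement) is not evidence of benefit.
2. In Protocol 12.2.1 and SAP 7.1, state that the conclusion for the primary objective rests on the planned overall mean percent change in spleen volume and TSS with 95% CI, read as uncontrolled change from baseline, and that r serves the dosing objective.
3. Add to SAP 7.1 a sensitivity partial correlation adjusted for baseline platelet count and the baseline value of the outcome. State that it reduces baseline confounding but does not remove post-baseline selection.
4. Reconcile the PGIC condition for going above 10 mg bid: the Synopsis and SAP 4.1 require a worsening category, whereas Protocol 8.6.1 accepts scores 3 to 7. Which patients can reach the top core-phase doses depends on it.

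Cost: text changes and one extra analysis of data already collected, with no new patients, visits or change of primary endpoint. Two covariates at n = 150 move the critical value from 0.160 to 1.976/√(146 + 3.906) = 0.161. The correlation loses inferential weight, and the mean remains an uncontrolled change, which matters most for open-label TSS.

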7.2.3. Secondary Endpoints

- Percent change in spleen volume at Week 24 compared to Baseline.
- Percent change in Total Symptom Score as measured by the modified MFSAF v2.0 diary at Week 24 compared to baseline.
- Proportion of subjects with $\geq 35\%$ reduction in spleen volume at Week 24 compared to baseline.
- Proportion of subjects with $\geq 10\%$ reduction in spleen volume at Week 24 compared to baseline.
- Proportion of subjects with $\geq 50\%$ improvement in total symptom score as measured by the modified MFSAF v2.0 diary at Week 24 compared to baseline.

- Long-term efficacy of ruxolitinib will be assessed by monitoring change and percent change in spleen length, as measured by palpation, and change in PGIC score from baseline to each visit where the variables are measured through Week 156.

7.3. Measures Taken to Avoid Bias

This is an open label study. Measurement of spleen volume by MRI (or CT scan in applicable subjects) and determination of thrombocytopenia grade (by CTCAE criteria) are objective responses.

7.4. Number of Subjects

Approximately 150 subjects may be enrolled.

7.5. Criteria for Study Termination

Both the Sponsor and the Investigator reserve the right to terminate the study, according to the terms specified in the study contract. The Investigator is to notify the IRB/IEC in writing of the study's completion or early termination, and send a copy of the notification to the Sponsor or Sponsor's designee and retain one copy for the site study regulatory file.

8. TREATMENT OF SUBJECTS

8.1. Treatment Arms and Study Drug Administration

All subjects will begin dosing at 5 mg bid ruxolitinib. Doses should be taken morning and evening, approximately 12 hours apart, and without regards to food.

Dose increases will be allowed for subjects with adequate platelet counts, and mandatory dose reductions and interruptions will be required for declining platelet counts, declining ANC levels or Grade 2 and higher hemorrhage events. See [Section 8.6](#), Dose Adjustments.

8.2. Treatment Compliance

Subjects will bring all bottles of unopened, empty, and opened/partially used study drug with them to each study visit. Investigative site staff will perform a count of returned pills to assess compliance, and this information will be entered on the eCRF. Study drug, including all bottles of unopened, partially opened or empty bottles cannot be returned to the depot until a monitor reviews and verifies all pill counts for compliance.

8.3. Randomization and Blinding

Not applicable, study is open label and single arm.

8.4. Duration of Treatment and Subject Participation

Participation will be for approximately 165 weeks and 2 days, including the screening and baseline phases (see [Section 9.1](#)), core treatment phase (see [Section 9.2](#)), extended treatment phase (see [Section 9.3](#)), and follow-up phase (see [Section 9.5](#)).

8.5. Considerations for Dose Modifications

Inhibition of JAKs by a JAK 1/2 inhibitor such as ruxolitinib is associated with thrombocytopenia and anemia in subjects with MF. See the Investigator's Brochure for additional details on hematologic consequences of JAK inhibition. Platelet count, ANC and hemoglobin levels will be assessed on a regular basis. Complete blood count (CBC) will be monitored more frequently in the first few weeks of the study, and more frequent monitoring may be done at the Investigator's discretion at any time.

8.6. Dose Adjustments

The goal of dose modifications in the study is to permit individual dose optimization for subjects to obtain maximum benefit, while maintaining a stable platelet count $> 25 \times 10^9/L$, and an ANC $> 0.5 \times 10^9/L$.

8.6.1. Dose Increases

Dose increases are optional.

During the core treatment phase, doses of ruxolitinib may be increased in 5 mg qd increments up to a dose of 10 mg bid starting at the Week 4 visit and at subsequent study visits. Dose increases can occur no more frequently than every 4 weeks, and only if:

- Platelet count was always $\geq 40 \times 10^9/L$ since the last scheduled study visit
- Platelet count, if decreased since the last scheduled study visit, is decreased by no more than 20% of the platelet count at the last scheduled visit
- No dose decreases or holds for safety have occurred during the preceding 4-week interval
- $ANC > 1.0 \times 10^9/L$ since the last scheduled study visit.
- For subjects with prior \geq Grade 2 hemorrhage events, please see below under [Section 8.6.3.4](#), Restarting with Resolution of Hemorrhage Events

Doses may not exceed 10 mg bid except in subjects who continue to meet the above dose escalation criteria, and who have, in addition, a PGIC score of 3 (minimally improved) to 7 (very much worse) while receiving 10 mg bid. Such subjects may continue dose escalation to a maximum dose of 15 mg bid. Note that when a 5 mg qd increment is added, creating a regimen such as 5 mg/10 mg, the higher dose should be taken in the evening and the lower dose in the morning.

During the extended treatment phase, doses of ruxolitinib may be increased in 5 mg qd increments up to a dose of 25 mg bid if the subject meets the above dose escalation criteria, or per the investigator's discretion.

Doses may never exceed 25 mg bid.

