| 
Study Drug, Dosage and Mode of Administration and dose adjustments:
 
All subjects will begin dosing at 5 mg bid ruxolitinib. Doses should be taken morning and evening, approximately 12 hours apart, and without regards to food.
 
During the core treatment phase, doses of ruxolitinib may be increased in 5 mg qd increments up to a dose of 10 mg bid starting at the Week 4 visit and at subsequent study visits (no more than every 4 weeks) if platelet count was always $\geq 40 \times 10^9/L$ since the last scheduled study visit, platelet count, if decreased since the last visit, is decreased by $\leq 20\%$, no dose decreases or holds for safety have occurred during the preceding 4 week interval, no \geq Grade 2 hemorrhage events have occurred since initiating treatment and ANC is $> 1000/\mu L$. Doses may not exceed 10 mg bid except in subjects who continue to meet the above dose escalation criteria, and who have, in addition, a PGIC score of minimally worse, much worse or very much worse while receiving 10 mg bid. Such subjects may continue dose escalation to a maximum dose of 15 mg bid.
 | | | | | | | | | | | |

During the extended treatment phase, doses of ruxolitinib may be increased in 5 mg qd increments up to a dose of 25 mg bid if the subject meets the above dose escalation criteria, or per the investigator's discretion.

Doses may never exceed 25 mg bid.

Subjects will be required to decrease the dose for platelet count $< 35 \times 10^9/L$, and to hold dosing for platelet count $< 25 \times 10^9/L$. Subjects will have the option to restart or re-escalate the dose with improving platelet count.

Subjects will be required to interrupt dosing for any Grade 2 or higher hemorrhage events. Subjects will be able to restart ruxolitinib dosing with resolution of Grade 2 events; restart after a second event requires review and discussion of pertinent data with the sponsor. Restarts of ruxolitinib will only be permitted in some cases of Grade 3 and 4 events, after review and discussion of pertinent data with the sponsor.

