8.6.3.4. Restarting with Resolution of Hemorrhage Event

- For Grade 2 hemorrhage events of any causality, dosing may be restarted at the prior level once the event is resolved to Grade 0, and its underlying cause has been alleviated or resolved, as long as platelet count and ANC do not preclude a restart at that dose level. Restart of dosing after a second Grade 2 hemorrhage event may only occur following discussion with the sponsor taking into account causality, resolution of the bleeding and underlying etiology and likelihood of recurrence, in order to reach agreement that the potential benefits of a restart at an appropriate dose outweigh risks of recurrent hemorrhage.
- For Grade 3 or 4 hemorrhage events of any causality, dosing may only be restarted provided: platelet count and ANC do not preclude a restart, the event has resolved to Grade 0, and the underlying cause has been alleviated or resolved, and following discussion with the sponsor taking into account causality, resolution of the bleeding and underlying etiology and likelihood of recurrence, in order to reach agreement that the potential benefits of a restart at an appropriate dose outweigh risks of recurrent hemorrhage. Further dose escalations in these subjects will also require discussion with the sponsor.

Note that if more than one finding (thrombocytopenia, neutropenia or hemorrhage) was the cause for the dose reduction or interruption, improvements in all parameters must be considered in restarting ruxolitinib and the lowest calculated dose must be used.

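### The protocol gives two different rules for core-phase dose increases: which PGIC scores allow more than 10 mg bid, and whether the dose may rise after a Grade 2 or higher hemorrhage

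*Protocol*

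**What the plan says.** Three places in the current protocol govern core-phase increases.

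- **Synopsis, dosage and dose adjustments.** An increase requires, among other conditions, that no ≥ "Grade 2 hemorrhage events have occurred since initiating treatment". Going above 10 mg bid, to at most 15 mg bid, also requires "a PGIC score of minimally worse, much worse or very much worse while receiving 10 mg bid".
- **Section 8.6.1.** The platelet, ANC and four-week conditions are in substance those of the synopsis. The hemorrhage bar is missing. In its place, subjects with prior ≥ "Grade 2 hemorrhage events, please see below under" Section 8.6.3.4. Going above 10 mg bid requires "a PGIC score of 3 (minimally improved) to 7 (very much worse) while receiving 10 mg bid".
- **Section 8.6.3.4.** After a first Grade 2 event, "dosing may be restarted at the prior level once the event is resolved to Grade 0", provided the cause has been dealt with and counts allow. After a second, restart needs sponsor discussion. After Grade 3 or 4, restart needs sponsor agreement, and "Further dose escalations in these subjects will also require discussion with the sponsor".

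The introduction to Section 8.6.3 adds that the "restarting and re-escalation doses in this section are the maximum allowed under this protocol". Appendix 5 numbers the PGIC from 1 (very much improved) to 7 (very much worse); 3 is minimally improved, 4 no change and 5 minimally worse. SAP Section 4.1 repeats the synopsis PGIC condition, but SAP Section 2 says the SAP was written for Amendment 1.

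**The concern.** These conditions decide which thrombocytopenic subjects, some of whom have already bled on treatment, may receive a higher dose. Two sites, each following a page of the same protocol, could treat the same subject differently, and a monitor could not say which of them had deviated.

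The same conditions limit the final titrated dose, which is one of the two variables in both co-primary correlations (protocol Section 12.2.1, SAP Section 5.9.3.1). The importance of the point rests on the contradictory dosing rule. It does not rest on demonstrated harm to the analysis.

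**Working it through.** The plan states no figure for this point. The check is a comparison of texts, followed by the doses each text allows.

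**1. PGIC condition.** Synopsis: {5, 6, 7}, 3 of 7 scores. Section 8.6.1: {3, 4, 5, 6, 7}, 5 of 7 scores. The difference is {3, 4}, 2 of 7. Section 8.6.1 prints both the numbers and their labels, so no reading of the scale reconciles the two.

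**2. Hemorrhage condition.**

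| Prior event on treatment | Synopsis | Sections 8.6.1 and 8.6.3.4 | Result |
|---|---|---|---|
| Grade 3 or 4 | No increase | Escalation possible after sponsor discussion | Contradiction |
| Grade 2 | No increase | Restart covered; nothing on a later rise above the prior level | Unclear |

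For Grade 2, the ceiling stated in the introduction to Section 8.6.3 can be read as agreeing with the synopsis, so this is an ambiguity and not a conflict. The note in Section 8.6.2 does not settle it. It says that "Dose re-escalation will follow the guidelines provided in" Section 8.6.1, which sends a subject with a prior bleed back to Section 8.6.3.4.

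**3. Dose reached by an otherwise qualifying subject with PGIC 3 or 4.** Assumptions: visit day = week × 7; every optional increase is taken up to 10 mg bid; steps are 5 mg/day, at least four weeks apart; a step at the Week 24 visit is ignored. SAP Section 5.9.3.1 averages the total daily dose over Days 141 to 168, which is 28 days.

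- Day 1: 10 mg/day. Week 4: 15. Week 8: 20 (10 mg bid). The first PGIC while on 10 mg bid is at Week 12.
- Synopsis: the dose stays at 20, so the average is at most 20 mg/day.
- Section 8.6.1, one step (Week 12, 16 or 20): 25 mg/day.
- Section 8.6.1, two steps (any two of Weeks 12, 16 and 20): 30 mg/day.
- Week 20 step taken at the end of its +5 day window (Day 145), so that 4 of the 28 days are at the lower dose: one step gives (4 × 20 + 24 × 25)/28 = 680/28 = 24.3; a second step gives (4 × 25 + 24 × 30)/28 = 820/28 = 29.3 mg/day.

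**4. Dose groups.** In the four-group efficacy shells of SAP Appendix B, 20, 24.3 and 25 all fall in >15 to 25, so one step changes no subject's group; 29.3 and 30 fall in >25. The six groups of SAP Section 5.2, which additional efficacy analyses may use, do separate 20 (>15 to 20) from 24.3 or 25 (>20 to 25). Subjects with PGIC 5 to 7 can reach >25 under both texts.

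**5. How many subjects.** Protocol Section 4.1.5 reports 53.7% with PGIC 1 or 2 at Week 24, leaving 100 − 53.7 = 46.3% scored 3 to 7 or not scored. This covers all doses, and scores 3–4 are not separated from 5–7. It gives neither the number affected nor a usable estimate of it. For the hemorrhage rule the documents give no relevant figure.

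**6. Effect on the test.** The dose comes from recorded dosing, so both correlations are defined under either text. The stated power and the critical correlation of 0.16 depend on n = 150, alpha and the assumed correlation, and do not change.

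**The case against.** The strongest reply is that this is an editorial lag with little consequence. PGIC is a one-item symptom rating, not a bleeding or platelet criterion. The platelet and ANC conditions, the mandatory holds and reductions, the withdrawal rules of Section 8.7.1 and the 15 mg bid core ceiling apply under both texts, and increases are optional. After a Grade 3 or 4 bleed no site can act alone: the sponsor must agree to a restart, must be consulted again before escalation, and must be notified within 24 hours (Section 11.7.2), with continuous monitoring behind that (Section 11.7.4). Sections 8.1, 8.6.2, 8.6.3.1 and 8.6.3.3 all point to Section 8.6 or 8.6.1 as the working rule. The synopsis PGIC wording nearly matches the SAP's Amendment 1 text, which suggests a line left behind.

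Much of this stands. The safeguards are real and limit the harm, and the SAP wording is not an error for the version it covers. The cross-references make Section 8.6.1 the likelier working text. But they do not say so: no text gives it precedence, and the synopsis cannot be dismissed as old, because the same entry carries the current 25 mg bid limit for the extended phase. Sponsor discussion after a Grade 3 or 4 event does not remove the synopsis bar; it leaves the sponsor deciding against a page of its own protocol. For PGIC 3 or 4 there is no such sponsor step, so a site would act alone.

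**Conclusion.** The concern holds. The current protocol contradicts itself on the PGIC range for exceeding 10 mg bid in the core phase, and on whether the dose may rise after a Grade 3 or 4 hemorrhage. After a Grade 2 hemorrhage the rule is unclear.

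Two of the seven PGIC scores are disputed. A subject in that range who takes the optional steps could have a final titrated dose of 25 or 30 mg/day (24.3 or 29.3 with a late Week 20 step) under Section 8.6.1, against at most 20 under the synopsis. This rests on the visit-day and step assumptions above. The number of such subjects cannot be derived, and no bias or loss of power is claimed. The point must be fixed because a dose-escalation rule in a population at risk of bleeding has to read the same wherever a site looks it up. Which rule is right is not judged here.

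**What to change.** Reconcile the synopsis with Sections 8.6.1 and 8.6.3.4, and with the introduction to Section 8.6.3, so that one PGIC range and one prior-hemorrhage condition hold throughout. The hemorrhage condition should say what applies after a Grade 2 event. The sponsor decides both. Until the amendment is in force, state which text governs and notify sites. Update SAP Section 4.1 to the current protocol at the same time.

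Optionally, count the core-phase steps above 10 mg bid made with PGIC 3 or 4 that met the shared platelet, ANC and four-week conditions with no prior Grade 2 or higher hemorrhage, and mark those subjects on the dose scatter plots planned in SAP Section 10.2. List increases after a Grade 2 or higher hemorrhage separately, without classing them as compliant with either text: Section 8.6.3.4 is silent after Grade 2, and these data do not record the sponsor discussion needed after Grade 3 or 4.

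The cost is protocol and SAP wording and one clarification letter. The optional count and listing use PGIC, hemorrhage, dosing, platelet and ANC data already collected.
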